7. STATISTICAL METHODOLOGY FOR SAFETY

Safety analyses will consider AEs and SAEs, according to their relationship with study treatment, as well as analytical results, deaths and the reasons for treatment discontinuations, delays and/or dose reductions. All AEs and SAEs will be graded according to NCI-CTCAE v.4., and they will be coded using the Medical Dictionary for Regulatory Activities (MedDRA).

Safety profiles will be described by bar charts. If serious toxicities happen, special follow-up -with descriptive statistics and graphs (boxplots, line plots) - will be made to find out the pattern of the event.

7.1. Toxicity and Adverse Events

All the AEs will be coded using the MedDRA.

The toxicity evaluation will be coded with the NCI-CTCAE v.4. Toxicities will be described according to the worst NCI-CTCAE grade.

Summary of overall AEs will be done by System Organ Class (SOC) and Preferred Term (PT), by severity (worst toxicity grade) and by relationship to the study drug. Tables will be sorted by SOC/PT coded with MedDRA.

A frequency table will be made for the AEs leading to cycle delay, dose reduction or withdrawal of study medication. AEs with outcome of death will also be presented by relationship to the study drugs.

7.2. Clinical Laboratory Evaluation

Laboratory results will be classified according to the NCI-CTCAE v.4.

The following hematological values (worst grade per patient and per cycle during treatment) will be displayed: white blood cells count (WBC), neutrophil count, lymphocyte count, platelet count and hemoglobin.

Overall cross tabulation will be presented for the worst grade during treatment vs. the baseline toxicity grading of anaemia, lymphopenia, neutropenia, leukopenia and thrombocytopenia.

If a grade 3/4 neutropenia or thrombocytopenia increase occurs during a treatment cycle, the first day the onset value is reached (counting from the start of the cycle) will be tabulated.

Time to recovery of the abnormality (i.e., grade 3/4 neutropenia or thrombocytopenia) will be assessed and defined as the time, in days, from the start of the grade 3/4 abnormality until the abnormality is recovered (grade ≤ 2). The analysis will be carried out taking into account all events, including those that occur in a same cycle. The information will be shown by means of median and range.

Likewise, the following biochemical values (worst grade per patient and per cycle during treatment) will be displayed: alanine aminotransferase (ALT), aspartate aminotransferase (AST), total bilirubin, direct bilirubin, alkaline phosphatase (AP), creatinine, creatinine clearance, calcium (corrected by albumin levels), potassium (K), sodium (NA), glucose and albumin.

Time to recovery of the abnormality (grade 3/4 AST or ALT) will be assessed and defined as the time, in days, from the start of the grade 3/4 abnormality until recovery to grade ≤ 2 . The analysis will be carried out taking into account all events, including those that occur in a same cycle. The information will be shown by means of median and range.

Overall cross tabulation will be presented for the worst grade during treatment vs. the baseline toxicity grading of biochemical abnormalities.

7.3. Vital Signs, Physical Examination, Left Ventricular Ejection Fraction and Electrocardiogram Findings

Summary tables will be prepared with the performance status, physical examination, body weight, left ventricular ejection fraction (LVEF) and electrocardiogram (ECG) abnormalities at baseline and during the treatment, if appropriate, for each patient.

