6.2.2. Secondary Endpoints

Time-to-event variables (DOR, PFS and OS) and their fixed time estimates will be analyzed according to the Kaplan-Meier method. Kaplan-Meier curves will be plotted.

For categorical variables, comparisons will be carried out by a Fisher exact test and a multivariate analysis by logistic regression. For time-to-event variables, comparisons will be carried out by a log-rank test and by a Cox regression analysis. No formal conclusions will be expected on these grounds. Exploratory comparisons will be performed at a 0.05 level.

If appropriate, exploratory multivariate models (main effects or including interaction terms) will include all prognostic factors/covariates widely reported and recognized by oncologists: age, age at diagnosis, baseline ECOG PS (Eastern Cooperative Oncology Group Performance Status), stage at diagnosis, Tumor primary location: right vs left side tumors; sites of metastasis; visceral vs non visceral, body mass index (BMI), body surface area (BSA), time from diagnosis to first infusion, time from diagnostic of metastatic disease to first infusion, prior advanced treatment lines, last prior therapy PFS, prior oxaliplatin exposure, KRAS status, BRAF-like expression, any relevant concomitant medication at baseline; EORTC-QLQ-C30 and QLQ-CPN20 score at baseline and other prognostic/predictive factors determined by the oncologist. The total number of variables included in the final model will always be in accordance with the number of events and the sample size, thus, whenever possible, no more than one variable per ten events will be included. The parameter estimates, hazard ratios and p-values of the variables retained in the model will be presented.

A sensitivity analysis for PFS including all treated patients will be performed. Event will be defined as progression or death irrespective of the subsequent therapies received for this analysis.

Waterfall plots will be used to describe the best variation of the sum of target lesions during treatment. Questionnaires scores over time will be described by time series charts, if appropriate.

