8.10. Imputation of Incomplete Dates

The dates of certain historical or current clinical activities are key component for statistical analysis. An incomplete date results from a missing day, month or year; in that case, the missing figure can be imputed allowing for the calculation of variables, such as duration and time to certain event. However, when all of them, day, month and year are missing no imputation will be done.

Before registration/treatment start

If the day of a month is unknown, then the imputed day will be the 15th of the month; if the month is also unknown, then the imputed date will be the 1st of July. This assumption will only be valid if the imputed date occurs earlier than the first dose administration date; otherwise the imputed date will be the first day of the month in which the first dose was administered (i.e. 01/ first dose administration month date/year).

Between treatment start and end of treatment

All date variables during treatment for which information is needed and is not fully available, for example AEs or concomitant medications, will be subjected to imputation by means of SAS programming. If the day of a date is unknown then the imputed day will be the 1st of the month, if the month and/or year are also unknown then the imputed date will be the 1st of January. This assumption will be valid if the imputed date is earlier than the treatment start date; otherwise, the imputed date will be the treatment start date.

After end of treatment

To ensure the most conservative approach for the time-to-event variables (i.e., DR, PFS and OS), which can be affected by missing values, the following rules will be implemented: if the day of a date is unknown then the imputed day will be the 1st; if the month is also unknown, then the imputed date will be the 1st of July. This assumption will be valid if the imputed date occurs later than the last drug administration date; otherwise the imputed date will be the date of the last drug administration plus the predefined cycle length (i.e., 21 days if PM060184), except if the patient dies before, in which case the date of death minus 1 will be used.

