8.12. Subgroup Analyses

If applicable, specific analyses for different subgroups determined by the following factors will be developed: prior oxaliplatin exposure, tumor primary location: right vs left side tumors, KRAS status, BRAF-like expression, MSI phenotype and other relevant factors determined by the oncologist.

No differentiation by center is planned.

8.13. *Methods for Handling Missing Data*

Missing values will not be included in the calculation of outputs.

8.14. *First Stage Analysis*

A futility analysis will be performed once the first 24 evaluable patients complete the Week 12 (± 5 days) tumor assessment; progress; die due to PD; or discontinue treatment due to unmanageable toxicity (whichever occurs first). If seven patients or more achieve PFS3, then 36 additional patients will be recruited (second stage).

8.15. *Identification of Fixed or Random Effects Models*

Not applicable.

8.16. *Data Analysis Conventions*

All data analysis conventions, data calculations and grouping needed to perform the statistical analysis will be described in a separate document.

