12.4.3. Laboratory abnormalities Over Time

Table 12.4.13 Evolution of hematological abnormalities from baseline, worst case per patient.

			Worst grade per patient						Total	
			0		1		...		N	%
			N	%	N	%	N	%		
Baseline*	Neutropenia	Grade 0								
		Grade 1								
									
	Grade 0								
		Grade 1								
									
	Thrombocytopenia	Grade 0								
		Grade 1								
									

(*) Defined as the last value recorded before or on the date of first infusion.

Table 12.4.14 Evolution of biochemical abnormalities from baseline, worst case per patient.

			Worst grade per patient						Total	
			0		1		...		N	%
			N	%	N	%	N	%		
Baseline*	AST increased	Grade 0								
		Grade 1								
									
	ALT increased	Grade 0								
		Grade 1								
									
	Grade 0								
		Grade 1								
									

(*) Defined as the last value recorded before or on the date of first infusion.

Table 12.4.15 Platelet count and neutrophil count time course pattern (summary).

Laboratory abnormalities	Onset day grade 3/4	Days with grade 3/4	Time to recovery*
			Median (range)
Platelet count			
Neutrophil count			

(*) Defined as the time, in days, from the start of the grade 3/4 abnormality until the abnormality is recovered (grade ≤ 2).

Table 12.4.16 ALT and AST time course pattern (summary).

Laboratory abnormalities	Onset day grade 3/4	Days with grade 3/4	Time to recovery*
			Median (range)
ALT			
AST			

(*) Defined as the time, in days, from the start of the grade 3/4 abnormality until the abnormality is recovered (grade ≤ 2).

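### Time to recovery of grade 3/4 laboratory abnormalities has no rule for events that have not recovered, so applying the SAP as written gives a median that is too short

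*SAP*

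**What the plan says.** SAP 7.2 defines time to recovery twice with the same construction. For neutropenia and thrombocytopenia it runs "from the start of the grade 3/4 abnormality until the abnormality is recovered", meaning grade ≤ 2. For AST and ALT it runs "from the start of the grade 3/4 abnormality until recovery to grade" ≤ 2. In both cases 7.2 adds: "The analysis will be carried out taking into account all events, including those that occur in a same cycle". The summary is then fixed: "The information will be shown by means of median and range".

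The footnote to Tables 12.4.15 and 12.4.16 (SAP 12.4.3) repeats the definition: "Defined as the time, in days, from the start of the grade 3/4 abnormality until the abnormality is recovered". The columns are onset day, days with grade 3/4, and time to recovery. None is for unrecovered or censored events.

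Three general rules bear on an event with no recovery date:
- SAP 6.2.2 names the variables that get a survival method: "Time-to-event variables (DOR, PFS and OS) and their fixed time estimates will be analyzed according to the Kaplan-Meier method". Time to recovery is not among them.
- SAP 8.10, on incomplete dates: "However, when all of them, day, month and year are missing no imputation will be done".
- SAP 8.13, on missing data: "Missing values will not be included in the calculation of outputs".

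SAP 8.16 sends remaining conventions and data calculations to a separate document, which is not supplied.

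**The concern.** Time to recovery is a time-to-event variable. It is known only when recovery has been seen. If sampling stops while the patient is still at grade 3/4 (death, clinical deterioration, new antitumor therapy, cutoff), all that is known is that recovery took longer than the time observed. Leaving such events out conditions the summary on recovery having been observed, which shortens the median. The top of the range is affected too, because it becomes the longest recovered event.

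These tables are where a reader will look to learn how long severe cytopenias and transaminase rises last. A median that is too short, with no count of unrecovered events beside it, gives no sign that anything has been left out.

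**Working it through.** The plan states no figure for time to recovery, so there is nothing to reproduce. The check is a reading of the rules, followed by an illustration of size.

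**Reading the rules together**
1. The end point exists only if grade ≤ 2 is observed (7.2; table footnote).
2. An event unrecovered at the last laboratory value therefore has no end date. 7.2 gives it no substitute value.
3. A wholly missing date is not imputed (8.10).
4. A missing value is left out of outputs (8.13).
5. No censored-data method is assigned to this variable (6.2.2), and the table shells have no place to count such events (12.4.3).

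The result is a median over recovered events, which does not fit the statement in 7.2 that all events count.

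**Where unrecovered events can arise**
- Protocol, Schedule of Assessments, note 6: clinically relevant, treatment-related grade ≥ 3 events are reassessed at least every 2–3 days until at least grade 2. Febrile neutropenia, grade 4 neutropenia and grade 4 thrombocytopenia are first checked daily.
- Protocol 5.3, Table 4: Day 1 of a later cycle requires ANC, platelet and AST/ALT values better than grade 3/4. Protocol 7.4 requires the laboratory tests within 2 days before dosing. A patient who starts another cycle therefore normally has recovery documented.
- This leaves mainly events in the last treatment period and events not judged treatment-related. The general reassessment rule and the post-treatment safety follow-up concern treatment-related events, whereas SAP 7.2 has no such restriction. The schedule shows no haematology or biochemistry in follow-up. End-of-treatment laboratory tests are required only if there are no data from the previous 10 days or the last data show a treatment-related alteration of grade ≥ 2 (Protocol 7.5). Missing that visit because of clinical deterioration is not a deviation.

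**Illustration 1: sampling stops early, independently of recovery**
The documents give neither the true median M nor the unrecovered share u. Both are assumed here: M = 5, 7 or 10 days and u = 10% to 50%.
- Recovery is exponential with rate λ = ln 2 / M.
- Censoring is exponential with rate c = λu/(1 − u), so the unrecovered share is c/(λ + c) = u.
- Among recovered events, time is exponential with rate λ + c = λ/(1 − u), so the recovered-only median is M(1 − u).

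| True median | u = 10% | 20% | 30% | 40% | 50% |
|---|---|---|---|---|---|
| 5 days | 4.5 | 4.0 | 3.5 | 3.0 | 2.5 |
| 7 days | 6.3 | 5.6 | 4.9 | 4.2 | 3.5 |
| 10 days | 9.0 | 8.0 | 7.0 | 6.0 | 5.0 |

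Simulation of 1,000,000 events per cell agrees; for M = 7 it gives 6.29, 5.60, 4.91, 4.20 and 3.50. In this model the relative shortfall equals u, and it is zero when u = 0.

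**Illustration 2: a fraction f never recovers**
Assume a recovered-only median of 7 days, so λ = ln 2 / 7. The median over all events is t = −ln(1 − 0.5/(1 − f))/λ. For f = 10%, 20%, 30% and 40% this gives 8.2, 9.9, 12.7 and 18.1 days, against a reported 7.

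**Illustration 3: ten events**
Seven recover on days 3, 4, 5, 6, 7, 8 and 9. Three are unrecovered at last samples on days 10, 14 and 21. The recovered-only median is 6 days. The Kaplan-Meier estimate falls by 0.1 at each recovery, from 0.9 on day 3 to 0.5 on day 7. Its median, taken as the first day at or below 0.5, is 7 days.

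**The case against.** The strongest reply is that no sentence in the SAP limits the statistic to recovered events. The specific statement in 7.2 says all events, and it could be held to prevail over the one-line general rule in 8.13. An ongoing event might be counted to its last assessment, and the separate conventions document (8.16) may say so. This stands in part: exclusion is what results from applying the rules together, not a declared intention. But the supplied text gives no other value for such an event, and the table shells show no sign of one.

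A reader might also infer that unrecovered events disappear from the report. They do not. They leave this one statistic and stay in the worst-grade tables and grade 3/4 listings (SAP 12.4.1 and 12.4.2) and in the individual laboratory listings. The summary worst-grade displays carry no duration, however, so they do not correct the median. The column for days with grade 3/4 might help, but the SAP neither defines it nor says how an ongoing event is counted in it.

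A reader might infer that the lost events are the most severe. The documents do not show this; an event can be unrecovered only because sampling ended.

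Finally, a large bias is tempting to claim. The reassessment schedule and the retreatment criteria speak against many unrecovered events, and Protocol 1.2.2 reports that haematological and biochemical abnormalities were not a major safety concern in earlier studies. That objection to size stands. It does not cover patients who die, deteriorate or start new therapy with a severe abnormality open, or ALT/AST rises not judged treatment-related.

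**Conclusion.** The point holds as a minor gap in a descriptive safety output. SAP 7.2 gives no rule for unrecovered events; applied with 8.10 and 8.13, it yields a median conditional on recovery, which is too short whenever some events are unrecovered. The direction is clear. The size cannot be set from the documents, because they give neither the unrecovered share nor a recovery time. It is probably modest, since the protocol's follow-up rules confine such events mainly to the last cycle and to events not judged treatment-related. The upper ends of the illustrations should not be read as a forecast.

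The conclusion assumes that an absent recovery date is treated as a missing value and that the conventions document does not say otherwise. The primary analysis of PFS3, the futility rule and the other efficacy endpoints are not affected.

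**What to change.** In SAP 7.2, state that an event not recovered to grade ≤ 2 by the last laboratory value, including before death, new antitumor therapy or cutoff, is censored at that value. Report the Kaplan-Meier median in place of the simple median. Add the number and percentage of events unrecovered to Tables 12.4.15 and 12.4.16.

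The cost is a sentence or two of SAP wording and one added column in each of two tables. No new data are needed, and Kaplan-Meier estimation is already planned for DOR, PFS and OS.

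There is a small downside. Several events from one patient are pooled, and censoring at death or new therapy may be informative. The estimate should therefore be labelled descriptive and always shown with the unrecovered count beside it. If nothing else is changed, the count alone would let a reader judge how far to trust the median.

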12.2.1. Display of Adverse Events

Table 12.2.1 Summary of AEs.

Category*	N (%)
Any AE	
Any drug-related AE	
Any grade 3/4 AE	
Any grade 3/4 drug-related AE	
Any treatment emergent AE* ²	
Any SAE in clinical database	
Any drug-related SAE in clinical database	
Any grade 3/4 SAE in clinical database	
Any grade 3/4 drug-related SAE in clinical database	
Deaths associated with AEs	
Deaths associated with drug-related AEs	
Treatment discontinuations associated with AEs	
Treatment discontinuations associated with drug-related AEs	

(*) Drug-related: AEs drug-related and unknown relationship.

(*²) excluding AEs present before drug administration and without increase in severity grade along the treatment.

Table 12.2.2 Treatment-related AEs. Worst grade by patient.

SOC	Preferred Term	Grade 1		...	Grade 4		All*	
		N	%		N	%	N	%
Blood and lymphatic system disorders	Anaemia Not Otherwise Specified (NOS)							
	...							
	...							
Cardiac disorders	Neuropathy peripheral							
	...							

(*) Any grade.

Table 12.2.3 Treatment-related AEs. Worst grade by cycle.

SOC	Preferred Term	Grade 1		...	Grade 4		All*	
		N	%		N	%	N	%
Blood and lymphatic system disorders	Anaemia NOS							
	...							
	...							
Cardiac disorders	Neuropathy peripheral							
	...							

(*) Any grade.

Table 12.2.4 Adverse Event regardless of relationship. Worst grade by patient.

SOC	Preferred Term	Grade 1		...	Grade 4		All*	
		N	%		N	%	N	%
Blood and lymphatic system disorders	Anaemia NOS							
	...							
	...							
Cardiac disorders	Neuropathy peripheral							
	...							

(*) Any grade.

Table 12.2.5 Adverse Event regardless of relationship. Worst grade by cycle.

SOC	Preferred Term	Grade 1			...	Grade 4		All*	
		N	%	...	N	%	N	%	
Blood and lymphatic system disorders	Anaemia NOS								
	...								
	...								
Cardiac disorders	Neuropathy peripheral								
	...								

(*) Any grade.

Table 12.2.6 Treatment emergent AEs. Worst grade by patient.

SOC	Preferred Term	Grade 1			...	Grade 4		All*	
		N	%	...	N	%	N	%	
Blood and lymphatic system disorders	Anaemia NOS								
	...								
	...								
Cardiac disorders	Neuropathy peripheral								
	...								

(*) Any grade.

Table 12.2.7 Treatment emergent AEs. Worst grade by cycle.

SOC	Preferred Term	Grade 1			...	Grade 4		All*	
		N	%	...	N	%	N	%	
Blood and lymphatic system disorders	Anaemia NOS								
	...								
	...								
Cardiac disorders	Neuropathy peripheral								
	...								

(*) Any grade.

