12.3. Serious Adverse Events and Deaths

12.3.1. Serious Adverse Events

Table 12.3.1 Treatment-related SAEs. Worst grade by patient.

SOC	Preferred Term	Grade 1		...	Grade 4		All*	
		N	%		N	%	N	%
Blood and lymphatic system disorders	Anaemia NOS							
	...							
	...							
Nervous system disorders	Neuropathy peripheral							
	...							

(*) Any grade.

Table 12.3.2 Treatment-related SAEs. Worst grade by cycle.

SOC	Preferred Term	Grade 1		...	Grade 4		All*	
		N	%		N	%	N	%
Blood and lymphatic system disorders	Anaemia NOS							
	...							
	...							
Cardiac disorders	Neuropathy peripheral							
	...							

(*) Any grade.

Table 12.3.3 SAEs regardless of relationship. Worst grade by patient.

SOC	Preferred Term	Grade 1		...	Grade 4		All*	
		N	%		N	%	N	%
Blood and lymphatic system disorders	Anaemia NOS							
	...							
	...							
Cardiac disorders	Neuropathy peripheral							
	...							

(*) Any grade.

Table 12.3.4 SAEs regardless of relationship. Worst grade by cycle.

SOC	Preferred Term	Grade 1		...	Grade 4		All*	
		N	%		N	%	N	%
Blood and lymphatic system disorders	Anaemia NOS							
	...							
	...							
Cardiac disorders	Neuropathy peripheral							
	...							

(*) Any grade.

Listing 12.3.5 Serious Adverse Events.

Patient id.	Preferred term code	AE reported (verbatim)	Status	Grade	Relationship	Onset date	Resolved date	Action	Serious criteria

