12.4.2. Biochemical Abnormalities During Treatment

Table 12.4.7 Biochemical abnormalities during treatment, worst grade per patient.

	N	Grade 1		...	Grade 4		All* ¹	
		N	%		N	%	N	%
ALT increased								
AP increased								
AST increased								
Creatinine increased								
Hyperglycemia								
Hypematremia								
Hypercalcemia* ²								
Hyperkalaemia								
Hypoglycemia								
Hyponatremia								
Hypocalcemia* ²								
Hypokalaemia								
Hypoalbuminaemia								
GGT increased								

(*¹) Any grade. (*²) Total plasmatic calcium corrected by albumin.

Table 12.4.8 Biochemical abnormalities during treatment, worst grade by cycle.

	N	Grade 1		...	Grade 4		All* ¹	
		N	%		N	%	N	%
ALT increased								
AP increased								
AST increased								
Creatinine increased								
Hyperglycemia								
Hypematremia								
Hypercalcemia* ²								
Hyperkalaemia								
Hypoglycemia								
Hyponatremia								
Hypocalcemia* ²								
Hypokalaemia								
Hypoalbuminaemia								
GGT increased								

(*¹) Any grade. (*²) Total plasmatic calcium corrected by albumin.

Listing 12.4.9 Grade 3/4 biochemical abnormalities. Worst grade per patient.

Patient id.	Test	Grade

Listing 12.4.10 Grade 3/4 biochemical abnormalities. Worst grade by cycle.

Patient id.	Cycle	Test	Grade

Listing 12.4.11 Biochemical tests not assessed per patient.

Patient id.	Lab. test

Listing 12.4.12 Biochemical tests not assessed by cycle.

Patient id.	Cycle	Lab. test

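### The SAP's on-treatment biochemistry tables omit the graded bilirubin and creatinine clearance results that SAP 7.2 promises, and its graded AE tables and severe-AE rows stop at grade 4.

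*SAP*

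**What the plan says.** **Laboratory results.** SAP 7.2 commits to showing the worst grade per patient and per cycle for a list of biochemical values that includes "total bilirubin, direct bilirubin, alkaline phosphatase (AP), creatinine, creatinine clearance". It also promises a cross-tabulation of worst against baseline grade for biochemical abnormalities. The shells are in SAP 12.4.2 ("Table 12.4.7 Biochemical abnormalities during treatment, worst grade per patient" and "Table 12.4.8 Biochemical abnormalities during treatment, worst grade by cycle") and SAP 12.4.3 ("Table 12.4.14 Evolution of biochemical abnormalities from baseline, worst case per patient"). Baseline grades are in Tables 11.1.23 and 11.1.27, and baseline values in Table 11.1.24.

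**Adverse events.** SAP 7.1 states: "Toxicities will be described according to the worst NCI-CTCAE grade". The AE shells (Tables 12.2.2 to 12.2.7) and the SAE shells (Tables 12.3.1 to 12.3.4, beginning with "Table 12.3.1 Treatment-related SAEs. Worst grade by patient") have columns from Grade 1 to Grade 4, followed by an any-grade column. Table 12.2.1 summarises severe events in rows such as "Any grade 3/4 drug-related AE", and Listings 12.2.8 to 12.2.13 are also limited to grade 3/4.

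**The concern.** The SAP text and its shells disagree about bilirubin. If the tables are programmed from the shells, a promised liver-safety result is lost although the data exist: protocol 7.4 collects bilirubin during treatment as part of Biochemistry-A. The result matters for this drug. Protocol 5.5.4 describes hepatic metabolism by CYP2C19 and CYP3A4, and protocol 1.2.2 describes negligible renal elimination. Patients with liver metastases may enter with ALT/AST up to 5 x ULN (protocol 4.1), and bilirubin is a treatment-continuation criterion on both Day 1 and Day 8 (protocol 5.3). Graded ALT and AST tables are hard to interpret for liver injury without bilirubin beside them.

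For fatal events the issue is the definition of the severe category. A reader normally takes the severe-AE row to cover everything from grade 3 upward. A row that stops at grade 4 can leave out a patient with the worst outcome, and the SAP does not say whether it does.

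**Working it through.** **Step 1. SAP 7.2 against Tables 12.4.7 and 12.4.8.** SAP 7.2 names 12 biochemical items.

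| SAP 7.2 item | Rows in each table |
|---|---|
| ALT, AST, AP, creatinine | 4 |
| Calcium, potassium, sodium, glucose (high and low) | 8 |
| Albumin (low) | 1 |
| Total bilirubin | 0 |
| Direct bilirubin | 0 |
| Creatinine clearance | 0 |
| GGT (not in the 7.2 list) | 1 |

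The total is 4 + 8 + 1 + 1 = 14 rows, which matches the shells. Nine of the 12 items are delivered, three are not, and one row was not announced. Neither table has an open row marked with dots, although the SAP uses such rows elsewhere, for example in Tables 12.2.2 and 12.4.14.

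**Step 2. Baseline.** Table 11.1.23 grades ALT, AP, AST and creatinine. Table 11.1.27 grades GGT, calcium, glucose, potassium, sodium and albumin. Neither grades bilirubin. Table 11.1.24 gives total and direct bilirubin as median and range only.

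**Step 3. Where on-treatment bilirubin could still appear.**
- "Listing 12.4.9 Grade 3/4 biochemical abnormalities. Worst grade per patient", and Listing 12.4.10 by cycle: the test column is free, so grade 3/4 bilirubin could be listed. Lower grades could not.
- Table 12.4.14: it has open rows, but only AST and ALT are named.
- AE tables: protocol 8.5.1 requires a laboratory abnormality to be recorded as an AE if it changes dosing, causes significant symptoms, leads to significant additional treatment, has a serious outcome, or is judged clinically relevant.
- Listing II.1.15: raw biochemistry values.

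Only the raw listing is certain to carry on-treatment bilirubin, and it is not a graded summary.

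**Step 4. Grade 5.** There are 6 AE tables (12.2.2 to 12.2.7) and 4 SAE tables (12.3.1 to 12.3.4). None of these 10 has a Grade 5 column. A fatal AE graded 5 would enter only the any-grade column, so the graded columns would not add up to it.

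**Step 5. Size of the effect on the severe-AE rate.** Let k be the number of patients whose only grade >= 3 AE is a fatal one, and N the number of treated patients (the safety set in SAP 4.3). The shortfall in the grade 3/4 row relative to grade >= 3 is k/N. The documents give no value for k, so the range is illustrative:
- k = 0: no shortfall
- N = 60: k = 1 gives 1/60 = 1.7 points; k = 2 gives 2/60 = 3.3; k = 3 gives 3/60 = 5.0
- N = 24 (stop after the first stage): k = 1 gives 1/24 = 4.2 points

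The figures 60 and 24 are evaluable patients (SAP 5.1 and 5.2). Evaluable patients are all treated and non-evaluable ones are replaced (SAP section 4), so the treated N is at least as large and the shortfall per patient at most these values.

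**The case against.** Three stronger readings are tempting, and the documents support none of them.

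- **That fatal events have no place in the safety outputs.** Table 12.2.1 has rows for deaths associated with AEs and with drug-related AEs. Table 12.3.6 gives cause of death, and Listings 12.3.7 and 12.3.8 list deaths and AEs with a fatal outcome. Tables 10.2.1 and 10.2.4 have rows for death due to toxicity, and SAP 7.1 promises fatal AEs by relationship. Nothing is hidden.
- **That the severe-AE rate will be understated.** The shortfall needs a patient with a fatal AE and no other grade 3/4 AE. Protocol 8.4 does not require progression, or signs clearly due to it, to be reported as AEs, which narrows that group. No decision rule uses this rate, and neither document says fatal AEs are graded 5.
- **That bilirubin is absent from the tables altogether.** Table 11.1.24 shows it at baseline, and the outlets in step 3 of the working remain possible. A rise that delays or omits a dose must be recorded as an AE, so many rises above the continuation limit should reach the graded AE tables.

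It can also be said that the shells are template text and the methods section governs. Some shells plainly are templates: peripheral neuropathy sits under cardiac disorders in several, and the dose-omission table has rows for delayed cycles. But Appendix I allows layout changes to suit group size, which does not clearly cover adding a missing parameter, and shells are what programmers work from.

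What stands after this is narrower. The graded bilirubin and creatinine clearance summaries promised in SAP 7.2 have no shell. Rises that change no dose, such as one first seen after the last dose, may appear only in raw listings. The separate death outputs do not correct the grade 3/4 count.

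**Conclusion.** The point holds as an inconsistency between SAP text and shells, together with an undefined severe category. On bilirubin and creatinine clearance it rests on a direct comparison and needs no assumption: three of the 12 promised items have no row in Tables 12.4.7 and 12.4.8, and bilirubin has no baseline grade.

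On fatal events it rests on one assumption, that fatal AEs are graded 5. The severe-AE rate can then be low by k/N: at most about 1.7 points per affected patient once 60 or more are treated, and zero if there is no such patient. The primary analysis and the stopping rule are unaffected. It should be corrected because the reported safety results can change and the edits are cheap.

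**What to change.** - Add rows for increased bilirubin to Tables 11.1.23, 12.4.7 and 12.4.8, and name bilirubin in Table 12.4.14.
- Reconcile creatinine clearance and GGT between SAP 7.2 and the shells, so that the text and the tables list the same parameters.
- Add a Grade 5 column to Tables 12.2.2 to 12.2.7 and 12.3.1 to 12.3.4, and state how fatal AEs are graded.
- Report grade >= 3 instead of grade 3/4 in Table 12.2.1 and Listings 12.2.8 to 12.2.13, and keep the separate death rows.
- Optionally, count patients with concurrent ALT/AST and bilirubin elevation from samples already collected. Neither document promises this, so it is an addition and not a correction.

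The cost is shell edits and minor programming, with no new data. The severe-AE rate may come out slightly less favourable.
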